3.4. Safety Endpoints

The following safety endpoints will be included in the analysis:

- Evaluation of adverse events (AEs) and serious adverse events (SAEs)
- Tolerability to the masked study drug will be solicited via questionnaire
- Changes from baseline in findings detected by best-corrected visual acuity (BCVA), biomicroscopy including corneal staining, intraocular pressure (IOP), and ophthalmoscopy
- Changes from baseline in corneal endothelial cell count (selected sites only; approximately 25% of study participants)
- Mean change from baseline in pupil diameter
- Changes from baseline in vital sign measurements
- Pregnancy test results (female participants of childbearing potential only)

3.5. Escape Medication

For participants with measured myopia progression ≥ 2.00 D from baseline in SE at a visit occurring between Month 18 and Month 36 (inclusive), and measurements obtained 6 months later at the next scheduled visit to confirm myopia progression (ie, confirmation at a visit between Month 24 and Month 42 [inclusive]), then treatment with escape medication (active SYD-101 0.03%) will be initiated at the confirmatory visit and continued until Month 48.

Participants on escape medication will adhere to the same visit schedule. No medications will be dispensed during or after the Month 48/End of Study (EOS) visit. As with masked study treatment, open-label SYD-101 0.03% (escape medication) will be provided by the sponsor, managed and tracked using IVRS/IWRS, and dispensed to participants by the assigned site staff.

4. General Statistical Considerations

All statistical analyses will be conducted using SAS Version 9.4 or higher (SAS Institute, Cary, North Carolina).

All statistical tests will be two-sided and will be performed at the 5% level of significance leading to 95% (2-sided) confidence intervals (CIs), unless otherwise stated. P-values will be rounded to 3 decimal places. If a p-value is less than 0.001 it will be reported as “<0.001.” If a p-value is greater than 0.999 it will be reported as “>0.999.”

Continuous data will be summarized by treatment group using descriptive statistics (number, mean, median, standard deviation (SD), minimum, and maximum). Categorical data will be summarized by treatment group using frequency tables (frequencies and percentages). Mean will be presented to one decimal place beyond the precision with which the data was captured. SD and median will be presented to two decimal places beyond the precision with which the data was captured. Minimum and maximum will be presented to the precision with which the data was captured. When count data are presented, the percentage will be suppressed when the count is zero in order to draw attention to the non-zero counts. A row denoted “Missing” will be included in count tabulations where specified on the shells to account for dropouts and missing values if needed. Unless otherwise noted, the denominator to determine the percentage of participants in each category will be based on the number of participants with available data. Select ordinal data may be summarized using both descriptive statistics and counts and percentages of participants in each category, as appropriate.

For measurements such as SE and axial length which are collected multiple times per eye, the per eye averages will be calculated from the available values for each eye and then the average value of the right and left eyes will be calculated. The average values will be presented as rounded to two decimal places in data listings, however no rounding will be performed prior to the final calculation of the average value for both eyes.

All study-related raw data that support the corresponding tables and figures will be presented in data listings. Additional data listings may be generated as needed. All table, listing and figure shells will appear in landscape format employing Courier New 9-point font. Unless otherwise noted, all tables will summarize participant results by treatment group sorted in the following order: Vehicle, SYD-101 0.01% and SYD-101 0.03%. After receipt of escape therapy or re-randomization, participants will be summarized under current treatment with the treatment group divided to show initial and current treatment (e.g., Vehicle to Escape, SYD-101 0.01% re-randomized to Vehicle, etc.). Unless otherwise noted, all data listings will be sorted by treatment group and participant identification number defined as investigator identification number concatenated with the participant number. Due to family relocation or site closure, participants could be transferred from one site to a different site. In such cases, participant identification number will remain unchanged. Participants who changed study sites will be included in a data listing.

The baseline value for an assessment is defined as the last non-missing measurement including unscheduled assessments before or on the day of treatment with study drug (Day 1). Change from baseline is defined as the post-baseline value minus the baseline value for the given

assessment. Please also see Section 9 for details regarding baseline considerations for safety analyses when participants receive more than one treatment.

When study day is used for display or in comparisons, the following algorithm will be used:

- study day = date of assessment - date of first dose +1,
if date of assessment \geq first dose date.
- study day = date of assessment - date of first dose,
if date of assessment $<$ first dose date.

Note that the date of first dose is Day 1 and the day before the date of first dose is Day -1 (for analysis, there is no Day 0 for study day). First dose refers to first dose of any study treatment unless otherwise specified.

For all efficacy and safety analyses, analysis visit windows will be used for assigning assessments to an analysis visit, as per [Table 4-1](#) below.

Table 4-1 Visit Windows

Scheduled Visit	Target Day	Analysis Visit Window (Days)
Screening	-21 to 1	Not applicable
Day 1	1	Not applicable
Week 2	14	2 to 52
Month 3	91	53 to 136
Month 6	182	137 to 231
Month 9	280	232 to 322
Month 12	364	323 to 409
Month 15	455	410 to 500
Month 18	546	501 to 591
Month 21	637	592 to 682
Month 24	728	683 to 773
Month 27	819	774 to 864
Month 30	910	865 to 955
Month 33	1001	956 to 1046
Month 36	1092	1047 to 1137
Month 39	1183	1138 to 1228
Month 42	1274	1229 to 1319
Month 48	1456	1320 to 1516

Visit Windows for Primary Analysis Endpoints

Scheduled Visit	Target Day	Analysis Visit Window (Days)
Screening	-21 to 1	Not applicable
Day 1	1	Not applicable
Month 6	182	2 to 273
Month 12	364	274 to 455
Month 18	546	456 to 637
Month 24	728	638 to 773 *Upper Limit M24 Cut Off
Month 30	910	774 to 1001
Month 36	1092	1002 to 1137 *Upper Limit M36 Cut Off
Month 42	1274	1138 to 1365
Month 48	1456	1365 to 1516

Only those assessments which are assigned to an analysis visit will be included in the summary tables and figures which are presented by visit. In the event, that there are multiple visits which fall into the same analysis visit window with non-missing data for an assessment and the visits include a scheduled and unscheduled visit(s), the assessment from the scheduled visit will be selected for analysis with one exception for BCVA. For BCVA, if there is a scheduled visit BCVA assessment and an unscheduled visit BCVA assessment in window performed on the same date, then the unscheduled visit BCVA assessment for that date will be used for analysis as it would be a re-test performed after refraction. If there are only unscheduled visit assessments performed within a window the visit closest to the target day of the study visit will be used for analysis. If there are two equal closest unscheduled visits occurring within the analysis visit

window (one before and one after the target day), then the earlier assessment will be used for analysis.

For summaries of an event at or before a given time point, such as progression at or before Month 24, all assessments (including unscheduled visits) on or before the Month 24 Visit or the upper limit of the corresponding visit window if no visit occurs in the Month 24 window, will be considered. All assessments will be presented in the data listings.

[figure not shown]
For a given participant, the Month 24 analysis will include all assessments (events, medications, etc.) with a start day on or before Month 24 Visit + 28 days (to allow for potential myopic progression confirmatory visit) for that participant or the upper limit of the Month 24 visit window (study day 773) + 28 days if no visit occurs in the Month 24 window. Participants who switch to escape therapy at the Month 24 visit will have all data included through the Month 24 visit. For participants whose first observed myopic progression >0.75 D is at the Month 24 visit and whose confirmatory visit cannot be scheduled within 28 days, the participants Month 24 data cut off will be extended to the date of their confirmatory visit.

For a given participant, the Month 36 analysis will include all assessments (events, medications, etc.) with a start day on or before the Month 36 Visit + 28 days (to allow for potential myopic progression confirmatory visit) for that participant or the upper limit of the Month 36 visit window (study day 1137) + 28 days if no visit occurs in the Month 36 window for that participant. The analysis at Month 48 will include all data in the database. (Observations after the upper limit of the Month 48 visit window for will be listed but excluded from analysis unless the participant was still receiving study medication.)

4.1. Sample Size

Group sample sizes of 280 in each treatment arm will achieve at least 90% power to detect a difference in the percentage of participants with myopic progression (>0.75 D) of at least 15% between a SYD-101 arm and Vehicle. Power calculations presented in Figure 4-1 are based on the Chi-squared test at a 2-sided significance level of 0.025.

[figure not shown]
Figure 4-1 Power for 2-Sided Chi-Square Test Evaluated at Alpha=0.025 for Proportion Responders When 280 Participants Per Arm

Additionally, group sample sizes of 280 per treatment arm achieves >90% power to detect a reduction of 0.18 D or more in the annual progression rate between SYD-101 and Vehicle, assuming a common SD of 0.60 D. Power calculations presented in

Figure 4-2 are based on a 2-sample t-test evaluated at the 0.025 significance level.

Figure 4-2 Power for 2-Sided T-Test Evaluated at Alpha=0.025 for Annual Progression Rate When 280 Participants Per Arm

Furthermore, to estimate the statistical power of the two region- specific primary endpoints, simulations based on various assumptions regarding the mean vehicle annual progression rate, the mean active annual progression rate based on % reduction from the vehicle annual progression rate, the SD for the APR as well as allowing for participant dropout/study treatment discontinuation and escape medication have been considered to investigate statistical power for a range of sample sizes. Simulations were run after the protocol was finalized to assess protocol sample size assumptions. For the most likely assumption of parameters examined, a mean placebo/control APR of 0.65 D and a mean active APR 0.325 D (a 50% reduction from the mean vehicle/control APR) both with a SD of 0.55 D and an annual dropout/study treatment discontinuation rate of 7%, a sample size of 217 participants per treatment arm provides an approximate 97% power for the FDA endpoint and an approximate 99.96% power for the EMA endpoint assuming a significant level of 0.025.

4.2. Randomization, Stratification, and Masking

Allocation to study treatment will occur in a double-masked manner on 2 occasions: initial randomization at Baseline (for Primary Treatment Period [Part 1]) and re randomization at Month 36 (for Randomized Withdrawal Period [Part 2]).

For Part 1, prior to initiation of study treatment, randomization will occur by site staff via the IVRS/IWRS once it is confirmed that the participant meets the final study entry criteria. The IVRS/IWRS will provide the participant identification number used on all study documents and will be used to manage the randomization and treatment assignment based on a stratified randomization scheme prepared by Sydnexis' designee. Initial randomization will be in a 1:1:1 ratio of SYD-101 0.01%: SYD-101 0.03%: Vehicle and stratified by baseline SE (0.50 D to 3.0 D and >3.0 D to 6.0 D) and age (3 years to <6 years, 6 years to <9 years, 9 years to <12 years, and 12 years to 14 years). Sites will also contact the IVRS/IWRS at the time a participant qualifies to initiate treatment with escape medication (ie, at confirmatory visit when measurements confirm progression of myopia ≥ 2.00 D in SE from baseline) for any participant who has qualified for escape medication.

For Part 2, to maintain masking, sites will contact the IVRS/IWRS at Month 36 for all participants. At Month 36, participants who were initially assigned (at Baseline) to SYD-101 0.01% (not on escape medication) will be re-randomized in a 1:1 ratio to masked SYD-101 0.01% or Vehicle; participants initially assigned (at Baseline) to SYD-101 0.03% (not on escape medication) will be re-randomized in a 1:1 ratio to masked SYD-101 0.03% or Vehicle. Re-randomization of SYD-101 participants will not be stratified. All participants who were initially assigned (at Baseline) to Vehicle (not on escape medication) will be re-randomized to masked SYD-101 0.03% at Month 36. Participants who have escaped to open label SYD-101 0.03% therapy at or prior to Month 36 will remain on escape therapy medication.

Masking of individual participant treatment assignments will be maintained throughout the study for all participants and site staff until the database is locked for the EOS analysis at Month 48.

Prior to the Month 24 database lock, all study team members at PPD, Santen, and Sydnexis will be masked to the treatment assignments, with the exception of the PPD randomization, IRT, and Clinical Supplies teams as their roles require access to the randomization and materials schedules.

Following the 24-Month database lock, PPD will send the study data and randomization code to Santen team members who will be responsible for running the statistical programs and producing the tables, listings, and graphs for the CSR. The data will be subset so that only observations through the Month 24 timepoint are included and only the initial randomization assignments will be provided. An independent medical writer will prepare the CSR and clinical modules of the MAA under Santen's supervision. Sydnexis will appoint a designee to review and approve the CSR who will not have day-to-day contact with any study sites. Santen team members will be unmasked and will not have any contact with study sites.

After the Month 36 database lock, the PPD Project Manager, PPD Oversight Director and the PPD Biostatistics and Programming team members as well as Sydnexis designees will become unmasked at the participant-level. Only the initial treatment assignments will be unmasked. The re-randomization of subjects at Month 36 will remain masked until the Month 48 database lock. The PPD Clinical team members responsible for monitoring participant data (Clinical Research Associates/Clinical Trial Managers), the PPD Medical Monitor, and Data Management team members, will remain masked to participant-level treatment assignments until after the Month 48 database lock. PPD will maintain separate access-controlled areas for the generation and distribution of the unmasked Month 36 analyses and will document team members who have access to these areas in the TMF.

Additionally, to minimize bias, results of the Month 24 analyses for EU submission will neither be made public, nor shared with study sites nor study monitors until after-Month 36 database lock; participant treatment assignments will remain masked until after the Month 48-lock. A masking plan will detail the names and roles of persons who will have access to the Month 24 and Month 36 aggregate data and participant treatment assignments.

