3.1. Overall Study Design and Plan

This is a 48-month, Phase 3, multicentered, randomized, double-masked, vehicle-controlled study to assess the safety and efficacy of SYD-101 eyedrops in male and female children between 3 and 14 years of age (inclusive) with myopia of 0.50 D to 6.00 D (inclusive). Clinical sites in the US and in Europe will participate in this study. A total enrollment of approximately 840 pediatric participants is planned for this study. The study will have 3 treatment groups: SYD-101 0.01%, SYD-101 0.03%, and the Vehicle of SYD-101.

Participants will be assessed according to the schedule of procedures and assessments.

Allocation to study treatment will occur in a double-masked manner on 2 occasions:

- initial randomization at Baseline (for Primary Treatment Period [Part 1]) will be in a 1:1:1 ratio of SYD-101 0.01%: SYD-101 0.03%: Vehicle and stratified by baseline spherical equivalent (SE, 0.50 D to 3.0 D and >3.0 D to 6.0 D) and age (3 years to <6 years, 6 years to <9 years, 9 years to <12 years, and 12 years to 14 years)
- re-randomization at Month 36 (for Randomized Withdrawal Period [Part 2]): participants who were initially assigned (at Baseline) to SYD-101 0.01% will be re-randomized in a 1:1 ratio to masked SYD-101 0.01% or Vehicle; participants initially assigned (at Baseline) to SYD-101 0.03% will be re-randomized in a 1:1 ratio to masked SYD-101

0.03% or Vehicle; all participants initially assigned (at Baseline) to Vehicle will be re-assigned to receive masked SYD-101 0.03%. Re-randomization of SYD-101 participants will not be stratified. Participants who have escaped to open-label SYD-101 0.03% therapy at or prior to Month 36 will remain on escape medication

There are 3 planned database locks for this study. The first will occur after all participants have completed the Month 24 visit and any required confirmatory visits for the purpose of submitting data for EU regulatory submission to the EMA (ie, Month 24 analysis). The second database lock will occur after all participants have completed the Month 36 visit and any required confirmatory visits for US regulatory submission to the FDA (ie, Month 36 analysis). The final database lock will occur after all participants have completed the last study visit (Month 48 or ET) to allow assessment of the persistence of effect of SYD-101 after 12 months of randomized withdrawal (ie, Month 48/Final analysis).

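### SAP 4.2 promises a Part 2 mask until the Month 48 lock, but releasing initial arms after the Month 36 lock discloses the Part 2 treatment of every Vehicle child; only the two SYD-101 arms keep a real mask

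*SAP*

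**What the plan says.** **What is unmasked, and to whom.** SAP 4.2 provides that after the Month 36 lock "the PPD Project Manager, PPD Oversight Director and the PPD Biostatistics and Programming team members as well as Sydnexis designees will become unmasked" at participant level. It limits this: "Only the initial treatment assignments will be unmasked". It then adds: "The re-randomization of subjects at Month 36 will remain masked until the Month 48 database lock".

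**Who stays masked.** The same paragraph lists the monitors and clinical trial managers, the Medical Monitor and Data Management; the list ends "Data Management team members, will remain masked to participant-level treatment assignments until after the Month 48 database lock". SAP 4.2 and Protocol 6.3 also keep participants and site staff masked to the Month 48 lock.

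**How Part 2 treatment is assigned.** SAP 4.2: "All participants who were initially assigned (at Baseline) to Vehicle (not on escape medication) will be re-randomized to masked SYD-101 0.03" (the 0.03% strength) at Month 36. SAP 3.1 says the same: "all participants initially assigned (at Baseline) to Vehicle will be re-assigned to receive masked SYD-101 0.03". Children who escaped at or before Month 36 stay on open-label SYD-101 0.03%. Each SYD-101 arm, apart from children on escape, is split 1:1 between its own dose and Vehicle.

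**A further masking statement.** The last paragraph of SAP 4.2 first withholds the Month 24 results from sites and monitors, then says "participant treatment assignments will remain masked until after the Month 48-lock".

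**The Month 24 rule.** At the Month 24 lock, the partner company's unmasked team may have no site contact, and the sponsor's reviewer of the study report may have no day-to-day site contact. No such rule is stated for the people unmasked at Month 36.

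**The concern.** A re-randomization can be hidden only where there is something random to hide. For Vehicle children the Month 36 step is a fixed switch to one treatment, so the initial code and the Part 2 code carry the same information. The SAP releases the first and says the second stays masked. For a third of the randomized children it cannot do both.

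The Month 36 lock comes after the last child's Month 36 visit, and the final lock after the last Month 48 visit. Part 2 is therefore still running for later enrollees when the codes are released. Two of the recipients, the project manager and the oversight director, hold management rather than analysis roles, and the site-contact restriction used at Month 24 is not repeated. At stake are an accurate description of masking in the study report and the handling of data on the Vehicle-to-0.03% group during its last year. Neither primary test is affected, because both primary datasets are locked by then.

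**Working it through.** The plan gives no figure for this. The check has two parts: what the initial arm tells a reader, and how many children it concerns.

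**1. Initial arm to Part 2 treatment** (SAP 4.2; Table 7-1 in SAP 7.3.1)

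| Initial arm | Part 2 treatment at Month 36 | Fixed by initial arm? |
|---|---|---|
| Vehicle, not on escape | SYD-101 0.03%, probability 1 | Yes |
| Vehicle, on escape | open-label SYD-101 0.03% | Yes, but no mask to lose |
| SYD-101 0.01%, not on escape | 0.01% or Vehicle, 1/2 each | No |
| SYD-101 0.03%, not on escape | 0.03% or Vehicle, 1/2 each | No |

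Table 7-1 shows no other Part 2 pattern for Vehicle. With 280 per arm, the fixed share is 280/840 = 1/3 of those randomized.

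Ignoring escape and dropout, someone who does not know the initial arm does best by guessing 0.03%, and is right with probability 1/3 + (1/3)(1/2) = 50%. Someone who knows the arm is right with probability (1 + 1/2 + 1/2)/3 = 67% overall and 100% for Vehicle children.

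**2. Vehicle children still in Part 2 when the codes are released**

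- Enrolment period: 70 − 48 = 22 months (study duration, Protocol 1.1).
- Assumed: uniform accrual; a lag L of 0 to 6 months between the last Month 36 visit and the lock. The documents give neither.
- Share still between Month 36 and Month 48 = (12 − L)/22.
- Retention to Month 36: SAP 4.1 uses 7% a year for dropout and treatment discontinuation combined. As a proxy, 0.93³ = 0.804, so 280 × 0.804 = about 225 Vehicle children.

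| Lag L (months) | Share in Part 2 | Of 280 | Of 225 |
|---|---|---|---|
| 0 | 12/22 = 55% | 153 | 123 |
| 2 | 10/22 = 45% | 127 | 102 |
| 4 | 8/22 = 36% | 102 | 82 |
| 6 | 6/22 = 27% | 76 | 61 |

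The range is about 60 to 125. Vehicle children on open-label escape must still be subtracted; the documents give no number for them. Dropout during Part 2 would lower the counts further. Protocol 5.5 encourages early group enrolment, which would also lower them. The recruitment delay from COVID-19 recorded in Protocol 11.4 leaves the accrual pattern uncertain.

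**The case against.** The case for leaving the text alone has real substance.

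- **The people who generate the data stay masked.** Sites, participants, monitors, trial managers, the Medical Monitor and Data Management are all covered. This stands.
- **A reader might infer that the rebound evidence is compromised.** The documents do not support that. The rebound analysis in SAP 8.3 uses SYD-101 children re-randomized to Vehicle, set beside SYD-101 children who were not. The initial arm does not say which of them switched, so the 1:1 mask is intact. The exposed group is outside that comparison, and all data after Month 36 are exploratory and descriptive.
- **A reader might infer that the unmasked managers decide per-protocol exclusions.** SAP 4.3.4 allows further exclusions at Month 48, but no section gives the project manager, oversight director or sponsor designees that role. SAP 5.2 has the clinical team track deviations under a written rules document.
- **A reader might see a flat contradiction between the participant-level unmasking and the closing sentence of SAP 4.2.** That sentence concerns sites and monitors, and its last clause can be read as limited to them. It is ambiguous rather than contradictory.
- **Month 36 has its own controls.** They include access-controlled areas, a record of who has access, and a separate masking plan. That plan is not among the documents and may restrict the designees further. Looser control once both primary analyses are locked is also defensible.

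None of this makes the Part 2 masking sentence true for the Vehicle arm. Nor does the SAP say why the project manager and oversight director need child-level codes while follow-up continues.

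**Conclusion.** The point holds as a limited one. After the Month 36 lock, the stated Part 2 mask is real for the two SYD-101 arms and absent, for the named unmasked roles, in the Vehicle arm. That conclusion follows from the assignment rule alone and needs no assumption. The size does: about 60 to 125 Vehicle children still in follow-up, less those on open-label escape, given uniform accrual over 22 months, a lag of 0 to 6 months and 7% annual loss used as a proxy.

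The consequence is confined to descriptive Part 2 data on the Vehicle-to-0.03% group and to the accuracy of the masking statement. It is a worthwhile correction, not a threat to either primary analysis or to the rebound comparison.

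**What to change.** Amend SAP 4.2, and align the masking plan with it:

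1. **Scope of the mask.** State that after the Month 36 lock the Part 2 mask holds only for children initially assigned to SYD-101, because an initial Vehicle assignment identifies the Part 2 treatment. State also that the closing clause on masking to the Month 48 lock applies to sites, participants and the roles listed as remaining masked.
2. **Access.** Extend the Month 24 rule, so that sponsor designees holding participant-level codes have no day-to-day site contact. Give the project manager and oversight director aggregate outputs only until the Month 48 lock. Statisticians and programmers keep participant-level codes inside the access-controlled areas that already exist.

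The change is to wording and access lists; design, sample size and analyses are untouched. The costs are that the two managers see participant-level listings later, and that the sponsor must choose designees without operational roles to work on the US submission.
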